6.1 General Design

This will be a prospective clinical trial designed to evaluate the incremental benefit of virtual FFR measured from CCTA, compared to invasive FFR and CCTA for the detection of flow-limiting coronary stenosis, as defined by invasive FFR ≤ 0.8 and vessel diameter of $\geq 2\text{mm}$.

572 consecutive patients who present to Lenox Hill Hospital Outpatient Clinics for CCTA due to chest pain or stable angina over a ten month period and meeting the study inclusion criteria are eligible for the study (Figure 1). Our team will employ CCTA-appropriateness criteria to ensure proper selection of patients, derived from the Appropriate Use Criteria for Cardiac Computed Tomography published in 2010 and jointly authored by multiple societies including ACCF, SCCT, and ACR [10]. FFR-CT measurements will be performed by a core laboratory in a blinded fashion. All eligible patients will undergo 64-slice or greater multi detector CCTA and CT-FFR measurements. The severity of the stenosis will be determined on site by level III CCTA readers. Patients with obstructive lesions of (30% to 100% stenosis) will receive Stress-MPI, per SOC protocol, and CT-FFR. Patients with positive Stress-MPI and CCTA (50% - 70%) or positive CCTA (71% to 100%) will undergo ICA with invasive FFR measurement in accordance to accepted guidelines and established practice standard. Those patients with invasively measured FFR ≤ 0.8 and with vessel diameter of $\geq 2\text{mm}$, or those who require revascularizations based on invasively estimated stenosis severity will be considered to have flow-limiting obstructive CAD, while the rest will be considered to have non-flow limiting obstructive CAD (if also $>50\%$ stenosis on ICA). If stenosis severity turns out to be $< 50\%$ after ICA (the gold standard), we will conclude that these patients have non-obstructive CAD. (Figure 1). Patients with 30% to 49% obstructive disease, according to CCTA, will be referred to optimal follow up care only. Any in this group who have positive CT-FFR will return for

ICA with invasive FFR measurement, and follow the protocol for those with 50% to 100% obstruction.

Figure 1:

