6.4 Primary Safety Endpoints

The study design evaluates the potential to substitute non-invasive for invasive FFR. Safety endpoints of the study include: 1. Evaluating the diagnostic accuracy of non-invasive FFR. If the end result demonstrates that the procedure is less accurate than invasive FFR, patients receiving this procedure, as an alternative to the current standard will be at greater risk. 2. Patients who undergo invasive procedures experience increased risk of infection or other comorbidities or complications, as compared to those who do not undergo invasive procedures. Therefore, if the noninvasive protocol results are not significantly different than the invasive results, patient safety might potentially be increased by using the noninvasive technology. 3. Noninvasive technology has the potential to reduce radiation exposure by reducing the number of invasive angiography and Stress MPI procedures necessary to complete patient evaluation. This increases patient safety relative to the adverse effects of radiation exposure.

7 Subject Selection and Withdrawal

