8.3 Method for Assigning Subjects to Treatment Groups

This is not a randomized study. Treatment assignments will follow the clinical protocol.

Once the CCTA results are interpreted by the physician, the physician will order CT-FFR exams for patients whose level of stenosis by CCTA standards is 30% to 100%.

If CT-FFR is positive patients will be referred for Cardiac Catheterization and invasive FFR.

If CT-FFR is negative, and level of obstruction is 30 to 49% by CCTA standards, patients will be referred to optimal medical care.

If CT-FFR is negative and level of obstruction is 50% to 70% by CCTA standards, patient will be referred for stress MPI. If stress MPI is positive patients will be referred for Cardiac Cath and invasive FFR. If stress MPI is negative, patients will be referred to optimal medical care.

If the patient has had a stress MPI within one year of the CCTA exam and the CCTA exam result is 50% to 70% obstructive, the physician will rely on the prior stress testing result, rather than repeating the stress test. If the stress testing results was negative, the patient will be referred to optimal medical care. If, in the investigator's opinion, the results indicate that the patient is at increased risk of obstructive disease, when considered with the CCTA findings, the patient will be referred to Cardiac Cath and Invasive FFR.

If CT-FFR is negative and level of obstruction is 70% to 100% by CCTA standard, patient will be referred to Cardiac Cath and Invasive FFR.

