*Patients who have borderline obstructive disease (50% to 70% stenosis) who have negative CT-FFR will be referred for Stress MPI to confirm, unless the patient has had stress testing within a year of the CCTA. This is an accepted practice as part of the standard of care at Lenox Hill Hospital. If the stress test is negative, the patient will be referred to his/her physician for follow-up. If the stress test is positive, the patient will be referred to Invasive Coronary Angiography for Invasive FFR and diagnostic cardiac catheterization. If the patient has had a history of negative stress testing within a year of the CCTA, then the patient will be referred to his/her physician for follow-up. If the patient's prior stress test had findings that, in the investigator's opinion, increase the patient's risk of obstructive disease when viewed with the CCTA findings, the patient will be referred to Invasive Coronary Angiography for diagnostic cardiac catheterization and Invasive FFR. This is an accepted practice as part of the standard of care at Lenox Hill Hospital.**

Patients who have borderline obstructive disease (50% to 70% stenosis) who have positive FFR will be referred for Invasive Coronary Angiography for Invasive FFR and diagnostic

*cardiac catheterization. This is an accepted practice as part of the standard of care at Lenox Hill Hospital. **

Patients with 71% or greater stenosis will be referred for Invasive Coronary Angiography for Invasive FFR and diagnostic cardiac catheterization. This is an accepted practice as part of the standard of care at Lenox Hill Hospital.

**In current standard of care practice at Lenox Hill Hospital, for borderline obstructive coronary disease, the decisions as to whether to proceed with stress testing or refer to invasive coronary angiography is left to the medical discretion of the attending cardiologist.*

Invasive Coronary Angiography and Invasive FFR are considered to be the gold standard procedures for evaluation of obstructive coronary artery disease. Patients deemed to be at high risk for obstructive disease based on CCTA or Stress testing are referred for invasive testing to determine whether cardiac intervention consisting of Percutaneous Coronary Intervention or Coronary Artery Bypass Graft is necessary.

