14.2 Statistical Methods

Statistical Aims

1. *To determine the sensitivity, specificity, positive predictive value (PPV) and negative predictive value (NPV) of the CCTA test (with or without stress MPI, as specified in Figure 1) + CT-FFR evaluation to identify chest pain patients with flow-limiting obstructive CAD. The ICA test will be used as gold standard.*
2. *To determine inter-observer reliability of CCTA and CCTA+CT-FFR test readings between an experienced and a non-experienced reader, and compare the results between CCTA and CCTA+CT-FFR; to determine the intra-observer reliability of CCTA and CCTA-FFR reading, for both the experienced and non-experienced reader, and for each reader compare the results between CCTA and CCTA+CT-FFR.*

3. To identify factors of return visit within 90 days in patients who had no ICA test or a negative ICA test result.

Outcome Variables

- *CCTA+CT-FFR test status (Positive/Negative). The test is deemed positive if ICA is required and negative if ICA is not required (see Figure 1).*
- *ICA (gold standard) test status (Positive / Negative). ICA is deemed positive if $FFR < 0.8$ and vessel diameter $>= 2\text{mm}$ or if the patient requires revascularizations based on invasively estimated stenosis severity. It is deemed negative otherwise.*
- *Return visit within 90 days (Y/N). Return visit is defined as patients who return for unplanned cardiac care, including emergency room visits, emergency hospital admissions, urgent percutaneous coronary intervention, coronary artery bypass graft, or acute myocardial infarction. Descriptive statistics (n, mean, median, standard deviation, IQR, frequencies and percentages) will be used to describe the demographic and clinical characteristics of the whole sample.*

For Aim 1, sensitivity, specificity, PPV, and NPV will be computed using the ICA result as the ‘true’ flow-limiting obstructive CAD status and the CCTA+CT-FFR test result as the ‘test’ status. Exact binomial 95% confidence intervals will be computed.

For Aim 2, inter- and intra-observer reliability for the CCTA and CCTA+CT-FFR tests will be assessed using Cohen’s Kappa coefficient. Dependent Kappa coefficients will be compared using a method developed by Donner et al .

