For Aim 3, a survival analysis regression model will be carried out to determine which risk factors are associated with “time-to-return visit”. Proposed factors will include age, sex, race, diabetes, hyperlipidemia, hypertension, active smoking and smoking history, family history of premature heart disease, obesity, and the number of cardiac risk factors present. In addition we will consider adding whether the admission was surgical or medical, and the MS or AP DRG case weight as a measure of severity.

Statistical Methods

Descriptive statistics (n, mean, median, standard deviation, IQR, frequencies and percentages) will be used to describe the demographic and clinical characteristics of the whole sample.

For Aim 1, sensitivity, specificity, PPV, and NPV will be computed using the ICA result as the ‘true’ flow-limiting obstructive CAD status and the CCTA+CT-FFR test result as the ‘test’ status. Exact binomial 95% confidence intervals will be computed.

For Aim 2, inter- and intra-observer reliability for the CCTA and CCTA+CT-FFR tests will be assessed using Cohen’s Kappa coefficient. Dependent Kappa coefficients will be compared using a method developed by Donner et al .

For Aim 3, a survival analysis regression model will be carried out to determine which risk factors are associated with “time-to-return visit”. Proposed factors will include age, sex, race, diabetes, hyperlipidemia, hypertension, active smoking and smoking history, family

history of premature heart disease, obesity, and the number of cardiac risk factors present. In addition we will consider adding whether the admission was surgical or medical, and the MS or AP DRG case weight as a measure of severity.

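### Aim 1 defines the composite test result as referral to ICA and uses ICA as the reference, so if the pathway is followed only PPV can be estimated

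*Combined protocol and SAP*

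**What the plan says.** Section 14.2 (Outcome Variables) defines the composite CCTA + CT-FFR result: "The test is deemed positive if ICA is required and negative if ICA is not required (see Figure 1". Aim 1 names ICA as the gold standard, and the methods text, which appears twice, says that "sensitivity, specificity, PPV, and NPV will be computed using the ICA result" as the truth, with exact binomial 95% intervals.

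The pathway decides who has ICA. In section 8.3: "If CT-FFR is negative, and level of obstruction is 30 to 49% by CCTA standards, patients will be referred to optimal medical care". For 50–70% stenosis with a negative CT-FFR, stress MPI follows, and "If stress MPI is negative, patients will be referred to optimal medical care". Section 9.2 sends patients below 30% stenosis to follow-up care. High-grade stenosis goes to ICA: section 6.1 says "positive CCTA (71% to 100%) will undergo ICA with invasive FFR measurement", and section 9 says "Patients with 71% or greater stenosis will be referred for Invasive Coronary Angiography".

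Section 6.4 puts this first among the primary safety endpoints: "Evaluating the diagnostic accuracy of non-invasive FFR". Sections 2 and 3.1 intend invasive FFR and 90-day outcomes to serve the evaluation of PPV and NPV. Section 14.3 promises unspecified adjustments for subjects who could not finish part of the study.

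**The concern.** The index test result is the decision to perform the reference test. A patient with a reference result is test-positive by definition, and a test-negative patient has no reference result unless someone departs from the pathway. Sensitivity and NPV need the number of diseased patients among test-negatives, and specificity needs the number of disease-free patients among them. The design supplies neither.

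The analysis as written would still produce a sensitivity of 100% with a narrow exact interval, which could be read as evidence that the strategy misses no flow-limiting disease. Section 6.4 ties patient risk to diagnostic accuracy, and Aim 1 is the only accuracy analysis in section 14.2. It also evaluates the composite strategy rather than CT-FFR, which is the test named in section 6.4.

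**Working it through.** **1. Reproduce the plan's figures (section 14.1).** Inputs: null rate 14%, alternative 6%, two-sided α = 0.05, power 80%; 60% of patients have CT-FFR and 35% of those have ICA.

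- n = [(1.960 × √(0.14 × 0.86) + 0.842 × √(0.06 × 0.94)) / 0.08]² = 120.99, so 121. This agrees.
- 121 / (0.60 × 0.35) = 576.2, against 576. This agrees.

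The powered quantity, negative ICA among patients who had ICA, is 1 − PPV.

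**2. Follow the branches (sections 8.3, 9 and 9.2).**

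| Branch | ICA | Composite result | Reference result |
|---|---|---|---|
| Below 30% | no | negative | none |
| 30–49%, CT-FFR negative | no | negative | none |
| 50–70%, CT-FFR negative, stress MPI negative | no | negative | none |
| 50–70%, CT-FFR negative, stress MPI positive | yes | positive | yes |
| Upper band (from 70% or 71%), any CT-FFR | yes | positive | yes |
| CT-FFR positive | yes | positive | yes |

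A stress test from the past year can replace the new one, and again leads either to ICA or to follow-up. Section 6.1 describes a somewhat different route, but because the test is defined by the need for ICA, the outcome is the same.

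**3. The expected table under full adherence (Clopper-Pearson 95%).**

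| Negative-ICA rate | TP / FP / FN / TN | Sensitivity | Specificity | NPV | PPV |
|---|---|---|---|---|---|
| 14% | 104 / 17 / 0 / 0 | 104/104 = 100% (96.5–100) | 0/17 = 0% (0–19.5) | 0/0 | 104/121 = 86.0% (78.5–91.6) |
| 6% | 114 / 7 / 0 / 0 | 114/114 = 100% (96.8–100) | 0/7 = 0% (0–41.0) | 0/0 | 114/121 = 94.2% (88.4–97.6) |

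**4. How many are unverified.** 576 − 121 = 455 (79%). With CT-FFR: 576 × 0.60 ≈ 346, and 346 − 121 = 225.

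**5. What a reported 100% could hide.** The documents give no disease rate in test-negatives, so these are assumptions. They take the 14% case and no flow-limiting disease below 30% stenosis.

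- 1% of the 225 diseased: 104 / (104 + 2.25) = 97.9%
- 5%: 104 / (104 + 11.25) = 90.2%
- 10%: 104 / (104 + 22.5) = 82.2%
- 20%: 104 / (104 + 45) = 69.8%

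The planned analysis returns 100% in each case.

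**6. A few off-pathway ICAs do not help.** Assume 5 ICAs in test-negatives, 1 of them positive. Sensitivity is 104/105 = 99.0%, specificity 4/21 = 19.0%, and NPV 4/5 = 80% (28–99.5). Five patients, probably selected by symptoms, would stand for 455.

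**7. Counting patients without ICA as reference-negative.** Specificity becomes 225/242 = 93.0% (CT-FFR patients) or 455/472 = 96.4% (all), but no false negative can occur, so sensitivity and NPV are 100% by assumption. Aim 3 also treats the two groups as distinct: "in patients who had no ICA test or a negative ICA test result".

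**The case against.** The best defence is that specificity is not hopeless. With 5–20% disease among the 225, it would lie between 214/231 = 92.6% and 180/197 = 91.4%, so a sensitivity analysis could bound it usefully. That is true, but it is a different analysis that imputes disease status in unverified patients. The plan does not contain it, and it does not rescue sensitivity or NPV.

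A second defence is that section 6.2 plans to correlate non-invasive with invasive FFR, so CT-FFR is compared directly with the reference. It is, but a correlation among patients who had ICA gives no sensitivity, specificity or NPV.

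Third, sections 2 and 3.1 mention 90-day outcomes for PPV and NPV. Section 14.2 uses them only in Aim 3. The adjustments in section 14.3 name no method, and patients managed without ICA according to the pathway have finished the study.

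Several points stand. The 5–20% range has no source in the documents; section 3.4 reports a CCTA false-negative rate below 1%, in emergency patients and so not directly transferable. The 60% in section 14.1 refers to 30–90% stenosis, whereas the pathway covers 30–100%, so the 121/225/455 split is approximate. Figure 1 is not available here, although the text describes the pathway. The primary endpoint and the sample size are untouched. The Aim 3 wording is supporting evidence only, since it does not define the Aim 1 reference. None of this alters the empty cells.

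**Conclusion.** The concern holds. As written, and with the pathway followed, Aim 1 can estimate the PPV of the composite strategy and nothing else. The conclusion follows from the definitions and does not depend on any assumed prevalence; assumptions enter only in judging how far a reported 100% sensitivity could be from the truth. The defect belongs to the composite strategy. CT-FFR itself has some verified negatives: patients with high-grade stenosis or a positive stress MPI have invasive FFR despite a negative CT-FFR. Aim 1 should be changed before analysis.

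**What to change.** In section 14.2, Aim 1:

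- **Composite strategy:** report PPV with its exact interval, and delete sensitivity, specificity and NPV against ICA.
- **CT-FFR:** add its own positive/negative result as an index test. Report sensitivity, specificity and NPV against ICA with invasive FFR only in the upper stenosis band, which is referred to ICA whatever CT-FFR shows. State how many patients there lack a CT-FFR reading or a completed ICA, and that the results apply to that band only. Note that the reference also counts revascularisation based on stenosis severity, and that section 8.9.1 gives study cardiologists access to CT-FFR.
- **Boundary:** the band starts at 71% in sections 6.1 and 9 but at 70% in sections 8.3 and 9.2. These must be reconciled.
- **Ninety-day events:** describe them in CT-FFR-negative patients without ICA as a clinical outcome, not as a reference for NPV, because the definition includes unplanned emergency visits. The roughly 230 patients below 30% stenosis (576 − 346) can be shown separately.
- **Sections 2 and 3.1:** align what they promise on PPV and NPV.

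The cost is wording only, on data already collected, but accuracy claims become narrower and less precise. The documents do not give the size of the upper band. Assuming it supplies 25–75% of the 121 ICAs (30–91 patients) at 14% negative, only 4–13 would be ICA-negative. A specificity near 75% would have an interval from 19–99% (3/4) to 46–95% (10/13), and a sensitivity near 85% from 65–96% (22/26) to 75–92% (66/78).

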In order to assess the primary endpoint of comparison of event rates for patients treated with CCTA and FFR-CT, we will perform a retrospective chart review of Invasive Coronary Angiograms performed at Lenox Hill Hospital from 2014 to 2018. We will specifically review Cardiac Catheterization reports to screen patients and record data for cases where the indication for Catheterization was (1) Positive stress test and/or (2) Positive CCTA. Based on the catheterization report we will determine whether the patient had obstructive coronary artery disease with/without flow limitation, in the same manner and following the same definitions as those used to categorize level of obstruction in subjects enrolled in the prospective cohort of the study. This data will be used as comparison/control group to assess trends and rates of invasive coronary catheterization when no intervention is necessary, in cases where CCTA and/or stress test without CT-FFR was used to determine the need for cardiac catheterization. Only the minimum amount of data required for a robust comparison of event rates will be collected.

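### Section 14.2 scores ICA positive only below FFR 0.8 while 6.1 includes 0.8 itself, and 8.3 and 9.2 place exactly 70% stenosis with negative CT-FFR in two referral bands

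*Combined protocol and SAP*

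**What the plan says.** **Reference standard.** Section 6.1 names the target condition as "flow-limiting coronary stenosis, as defined by invasive FFR ≤ 0.8 and vessel diameter of" at least 2 mm. It repeats the cut-off when classifying patients: "Those patients with invasively measured FFR ≤ 0.8 and with vessel diameter of" at least 2 mm, or who need revascularization on invasively estimated severity, count as flow-limiting. Section 14.2 defines the analysis variable differently: "ICA is deemed positive if $FFR < 0.8$ and vessel diameter" is at least 2 mm, or if revascularization is required. Of any other result it says "It is deemed negative otherwise".

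**Index test.** Section 14.2 takes the index result from the referral decision: "The test is deemed positive if ICA is required and negative if ICA is not required (see Figure 1").

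**Referral bands.** Section 6.1 states: "Patients with positive Stress-MPI and CCTA (50% - 70%) or positive CCTA (71% to 100%) will undergo ICA with invasive FFR measurement". Section 9 also starts direct ICA at 71%. Section 8.3 sends CT-FFR-negative patients to stress MPI at 50% to 70% and to catheterization at 70% to 100%. Section 9.2 has the same overlap, with 50% to 70% for MPI and 70% or more for catheterization.

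**Chart review.** Section 6.1 says the retrospective control group is classified "following the same definitions as those used to categorize level of obstruction in subjects enrolled in the prospective cohort of the study".

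**The concern.** Both sides of the Aim 1 two-by-two table rest on these thresholds: the referral rule produces the index-test result and the FFR cut-off produces the reference result.

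The cut-off decides whether a non-revascularized patient at exactly 0.80 is a true or a false positive. That feeds the PPV and the negative-ICA rate on which 14.1 bases the sample size. It does not feed the Section 6.2 event, which is ICA with no intervention needed and makes no use of the FFR value.

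The 70% overlap is first a matter of care: the text gives one patient two instructions, one of them invasive. It also matters for analysis. If the stress result is negative, the MPI route ends without ICA and the patient is test-negative. The catheterization route makes the same patient test-positive.

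**Working it through.** **1. The plan's own figures.** Inputs from 14.1: negative-ICA rate 14% (null) and 6% (alternative), two-sided 0.05, 80% power, one-sample chi-square; 60% of CCTA patients receive CT-FFR and 35% of those have ICA.

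n = [(1.960·√(0.14·0.86) + 0.842·√(0.06·0.94)) / (0.14 − 0.06)]² = 120.99, so 121. Completers: 121 / (0.60·0.35) = 576.2, against 576 in the plan. Both figures reproduce and are not in dispute.

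**2. The cut-off, side by side** (vessel at least 2 mm, revascularization not required):

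| Invasive FFR | Section 6.1 | Section 14.2 |
|---|---|---|
| below 0.80 | flow-limiting | positive |
| exactly 0.80 | flow-limiting | negative |
| above 0.80 | not flow-limiting | negative |

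Only the middle row differs. A patient who needs revascularization is positive under both.

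**3. Effect per patient.** One patient in 121 is 1/121 = 0.83 percentage points of the negative-ICA rate. If everyone for whom ICA is required undergoes it, the PPV is the complement of that rate and moves equally in the other direction, so these are one effect, not two.

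**4. Illustration against the planned test.** z = (X/121 − 0.14) / √(0.14·0.86/121), where X is the number of negative ICAs. At 6%, the expected X is 121·0.06 = 7.3.

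| X | z | two-sided p | PPV (exact 95% CI) |
|---|---|---|---|
| 7 | −2.60 | 0.009 | 94.2% (88.4 to 97.6) |
| 9 | −2.08 | 0.038 | 92.6% (86.3 to 96.5) |
| 10 | −1.82 | 0.069 | 91.7% (85.3 to 96.0) |

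The test rejects in the lower tail at 9 or fewer. Starting from 7, two reclassified patients leave the conclusion unchanged and three do not. The starting count of 7 and the number reclassified are both suppositions.

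**5. Exactly 70% stenosis, CT-FFR negative:**

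| Section | Instruction |
|---|---|
| 6.1 | ICA only if stress MPI is positive (direct ICA from 71%) |
| 9 | stress MPI first (direct ICA from 71%) |
| 8.3 | stress MPI, and also catheterization |
| 9.2 | stress MPI, and also catheterization |

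If stress MPI is positive, every route ends in ICA. The index result differs only when stress MPI is negative, whether done now or relied on from the previous year.

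**The case against.** **Few patients, evident intent.** The cut-off touches only patients at exactly 0.80 who do not need revascularization, and the overlap only CT-FFR-negative patients read at exactly 70%. Section 6.1 writes ≤0.8 twice, so 14.2 looks like a slip. The sign could also have been lost in reading the PDF, although the same sentence keeps its greater-or-equal sign for vessel diameter. All this limits the weight of the point. It does not remove it, because 14.2 is the text an analyst would program from.

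**Figure 1.** Section 14.2 refers to it for the index test, and Section 9 refers to it and Appendix 1 for procedures. Neither was available, and either may settle the 70% routing. The wording of 8.3 and 9.2 would still need correcting. Section 14.2 does not refer to Figure 1 for the FFR cut-off.

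**Stronger readings that the documents do not support:**

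- A reader might infer that the rules conflict for CT-FFR-positive patients at 50–70%, since 6.1 gives a CT-FFR route to ICA only at 30–49% and says "Patients with obstructive lesions of (30% to 100% stenosis) will receive Stress-MPI, per SOC protocol, and CT-FFR". But 8.3, 9 and 9.2 agree that positive CT-FFR leads to ICA, and the MPI sentence is qualified by standard of care. Section 6.1 also has CT-FFR-positive patients at 30–49% join the pathway of the higher bands. It is an incomplete summary, not a competing rule.
- A reader might infer that the chart review could be classified by a different cut-off from the prospective cohort. The chart-review text sits in 6.1 and points to graded obstruction categories. Those are defined only there, with ≤0.8, so the natural reading is ≤0.8.
- A reader might infer that the result is likely to reverse or that power is lost. The documents give no count at exactly 0.80, and they do not say which cut-off underlies the 14% and 6%. Aim 1 is estimation with confidence intervals and sets no success threshold.

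**Conclusion.** The point holds for two thresholds as written. The reference-standard cut-off in 14.2 does not match 6.1, and exactly 70% stenosis with negative CT-FFR has two instructions in 8.3 and 9.2. The first is clear from the text, assuming the inequality sign was read correctly. The second is clear as a conflict of wording, and whether it leaves the routing undetermined depends on Figure 1.

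The size is 0.83 percentage points of negative-ICA rate or PPV for each patient reclassified by the cut-off, assuming the planned 121 ICAs. The number of such patients, and of patients at exactly 70%, cannot be obtained from the documents. The step from 9 to 10 negatives shows how close the planned test's boundary lies to its expected count; it is not a forecast. The planned N, power and method are unaffected. It should be corrected because the change is free and settles how patients are classified and routed.

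**What to change.** - Set the ICA outcome variable in 14.2 to FFR ≤0.8, matching 6.1, and name it as the single definition for both the prospective cohort and the chart review. Do this before outcome data are examined.
- If outcome data have already been seen, report the negative-ICA rate and PPV under both cut-offs. Moving to ≤0.8 can only lower the negative count, so it should not be adopted alone after the fact. Section 14.1 already mentions 18 enrolled patients who were screen failures, which suggests that recruitment has started.
- In 8.3 and 9.2, use 50–70% for stress MPI and 71–100% for direct catheterization, as 6.1 and 9 do, and check that Figure 1 agrees.
- As a minor point, word 6.1 to include the CT-FFR-positive route to ICA that 8.3, 9 and 9.2 already state.

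The cost is wording in 6.1, 8.3, 9.2 and 14.2. No new patients or tests are needed. The second cut-off, if required, is one extra tabulation of data already held, provided the FFR values themselves were recorded.
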